8.5.2 Dispensing

The Sponsor will be responsible for providing the study drugs either Ciprofloxacin[®] Tablets (Ciprofloxacin/Metronidazole) or Ciprofloxacin Tablets & Metronidazole tablets to the patients in a quantity enough to be used till the end of the study and will record the patient's number and initials.

8.6 Risks & Benefits of study drug

Benefit: Ciprodiazole[®] (Ciprofloxacin & Metronidazole) is active against a broad spectrum of aerobic/anaerobic bacteria. So, it is indicated in pelvi-abdominal infections and/or following IV antibiotics in post-operative period, for pelvi-abdominal surgeries or acute conditions, it will be supplied by the sponsor.

Risk: The most frequently reported side effects of ciprofloxacin are nausea, diarrhea, liver function tests abnormality, vomiting, and rash.

The most common side effects of Metronidazole are allergic reactions such as skin rash, swelling of the face, lips, tongue or throat, fever or difficulty in breathing.

8.7 Discontinuation and Modification of Dosing of Ciprodiazole[®]:

- The usual dose should be reduced in patients with severe renal disease
- In the event that a positive result is obtained on a pregnancy test for a patient, the administration of Ciprofloxacin and Metronidazole must be discontinued immediately.

8.8 Concomitant Medication:

Throughout the study, Investigators may prescribe any concomitant medications or treatments deemed necessary to provide adequate supportive care except for those listed in the exclusion criteria. If these are required, the participant will be withdrawn. A medication, other than the study medication (Ciprofloxacin or Metronidazole) taken during the study will be recorded in the CRF.

Any medication or vaccine (including over-the-counter or prescription medicines, vitamins and/or herbal supplements) that the subject is receiving from 2 weeks prior to study drug administration and during the study, must be recorded in the paper case report form along with the reason for use, date(s) of administration including start and end dates, and dosage information including dose, route and frequency.

The investigator should review all concomitant medications for any potential interactions.

Ciprodiazole[®] Tablets (Ciprofloxacin hydrochloride & Metronidazole) is contraindicated with administration of tizanidine, because this may cause low blood pressure and sleepiness

Ciprodiazole[®] Tablets is contraindicated with administration of antacids containing magnesium and aluminum, supplements and other products containing calcium, iron or zinc because they reduce the effect of Ciprofloxacin.

Metronidazole potentiates the anticoagulant effect of Warfarin and other oral coumarin anticoagulants resulting in a prolongation of prothrombin time.

The simultaneous administration of drugs that induce microsomal liver enzymes, such as Phenytoin or Phenobarbital, may accelerate the elimination of metronidazole while the simultaneous administration of drugs that decrease microsomal liver enzymes activity, such as ceftrimide, may prolong the half-life and decrease plasma clearance of metronidazole.

Ciprofloxacin may increase the effects of caffeine.

Serious and fatal reactions have occurred when Ciprofloxacin was taken in combination with theophylline. These reactions have included cardiac arrest, seizures, status epilepticus, and respiratory failure.

Tendon disorders (tendinitis) have been rarely encountered in some cases related to concomitant use of quinolone with corticosteroids.

9 Research Question & Study Objectives

9.1 Primary Objective:

9.1.1 Primary Safety:

To compare safety of oral Ciprodiazole[®] tablets (Ciprofolxacin/Metronidazole) versus currently used Ciprofloxacin Tablets & Metronidazole tablets in pelvi-abdominal infections, either non-operative or post-operative following IV antibiotics.

9.1.2 Primary Efficacy:

To compare efficacy of oral Ciprodiazole[®] tablets (Ciprofolxacin/Metronidazole) versus currently used Ciprofloxacin Tablets & Metronidazole tablets in pelvi-abdominal infections, either non-operative or post-operative following IV antibiotics

9.2 Secondary Objective:

9.2.1 Secondary Safety:

- Presence of any signs/symptoms of post-operative wound infection such as redness, fever or wound discharge.
- Presence of undesirable effects on total leukocyte count and liver enzymes (SGOT & SGPT)

9.2.2 Secondary Efficacy:

- To compare the complete resolution or improvement of Pelvi-abdominal infection between ciprodiazole[®] versus combined treatment, based on pelvi-abdominal ultrasound and others
- To compare the days for complete healing of post-operative wounds between ciprodiazole[®] versus combined treatment

10 Research Methods

10.1 Study Design:

This is a single center, open Label, controlled, interventional phase IV Study conducted in Menoufia University Hospital in Egypt to compare the safety and efficacy of oral Ciprodiazole[®] tablets (Ciprofloxacin/Metronidazole) versus currently used Ciprofloxacin Tablets & Metronidazole tablets in pelvi-abdominal infection and following IV antibiotics in post-operative period, for pelvi-abdominal surgeries or acute conditions

This study is a clinical trial that will enroll 312 patients, who had pelvi-abdominal infection and/or started IV antibiotics for 48 hours, post-operative or till be able to tolerate oral intake in post-operative period, for pelvi-abdominal surgeries. They will be divided into two

treatment groups; group A: patients are treated with Ciprofloxacin[®] tablets (Ciprofloxacin/Metronidazole) and group B (control group): patients are treated with the currently used Ciprofloxacin Tablets & Metronidazole tablets, using computer-generated randomization list, generated by the Data Management department (DM) of the CRO (Nagy Research) for the 2 groups who will be enrolled in this study will agree to the release of information and sign an informed consent. Subjects included in this study are enrolled for the collection of data that reflect the care they receive under routine clinical circumstances. All provided care should be according to protocol and the local standard of medical care.

The screening and enrollment period is planned to be 12 months. Subject will start receiving the treatment for a duration not exceeding 15 days. And with post-operative cases, subject will start receiving the treatment after IV antibiotics for 48 hours or till be able to tolerate oral intake. Follow up will be for 15 days from enrolment till End of treatment.

10.2 Study Setting:

Subjects will consent to the collection of study related information while on the study. Subjects will be informed that data will be collected about their health while they are enrolled in this study. They may choose to withdraw at any time. Subjects will be advised that data collected in this study will be provided to the Sponsor, and may be reported to regulatory authorities or published in scientific journals. In any of these events, the subjects' identities will not be revealed.

10.2.1 Inclusion Criteria:

Subjects meeting all of the following criteria will be considered for enrollment in the study:

1. Egyptian male and female patients aged between 18-65 years' old
2. Subjects having pelvi-abdominal infections such as and not limited to: Ulcerative colitis, Diverticulitis, Cholecystitis, and PID (e.g oophoritis and salpingo-oophoritis).
3. Subjects during post-operative period for pelvi-abdominal surgery and following IV medication with Metronidazole injection plus third generation cephalosporin.
4. Subjects who are willing to sign Informed Consent Form (ICF) and ready to comply with the protocol for the duration of the study

10.2.2 Exclusion Criteria:

Subjects presenting with any of the following will not be included in the study:

1. Subjects with a history of hypersensitivity to any of the active ingredients of the treatments used
2. Subjects who are receiving or received any other antibiotics during the previous two weeks, rather than IV treatment in the first post-operative 48 hours, mentioned in the protocol (Metronidazole injection plus third generation cephalosporin)
3. Subjects with Pelvi-abdominal infection and performed surgery after failure of oral antibiotics.
4. Subjects having surgeries such as colorectal surgeries, appendectomy and ovarian cystectomy
5. Subjects with any medical condition requiring the usage of the following medications:

- a. Drugs that induce microsomal liver enzymes, such as Phenytoin or Phenobarbital, may accelerate the elimination of metronidazole
 - b. Drugs that decrease microsomal liver enzymes activity, such as cefrimide, may prolong the half-life and decrease plasma clearance of metronidazole.
 - c. Administration of theophylline in combination with Ciprofloxacin may lead to cardiac arrest, seizures, status epilepticus, and respiratory failure
 - d. Administration of corticosteroids in combination with Ciprofloxacin may lead to tendinitis
 - e. Antacids containing magnesium and aluminum, supplements and other products containing calcium, iron or zinc as they reduce the effect of Ciprofloxacin.
 - f. Tizanidine because this may cause low blood pressure and sleepiness
6. Subjects with uncontrolled diabetes mellitus; FBG > 200 mg/ml
 7. Subjects with renal impairment (S. Creatinine > 1.5 mg/dL)
 8. Subjects with hepatic impairment (Child-Pugh Score B-C)
 9. Subjects with liver enzymes (SGOT, SGPT) > 2 times Normal range.
 10. Pregnant or breast feeding women

10.2.3 Discontinuation/Withdrawal of participants from the study:

Each participant has the right to withdraw from the study at any time.

In addition, the investigator may discontinue a participant from the study at any time if the investigator considers it necessary for any reason including:

1. Ineligibility (either arising during the study or retrospective having been overlooked at screening)
2. Significant protocol deviation
3. Significant non-compliance with treatment regimen or study requirements
4. Disease progressions which requires discontinuation of the study medication or results in inability to continue to comply with study procedures.
5. Consent withdrawn by subject.
6. Lost to follow up
7. SAE or death
8. If a female subject becomes pregnant
9. Subjects which have Cholecystitis and it will be operated upon.

The reason for withdrawal will be recorded in the CRF. If the participant is withdrawn due to an adverse event, the investigator will arrange for follow-up visits or telephone calls until the adverse event has resolved or stabilized.

10.2.4 Assessments to be done:

1- Screening Visit Assessments:

- The enrollment period will be 12 months including the screening visit. Screening assessments will be completed and treatment will be initiated within visit 1.
- During this visit, patients will be screened for fulfillment of the inclusion and exclusion criteria and written informed consent will be obtained.
- Screening assessments will include physical examination, medical history, patient demographics, vital signs, concomitant medications, safety laboratory tests

(including Fasting Blood Sugar (FBS), Total leukocyte count, Liver enzymes (SGOT & SGPT), Total Bilirubin and S. Creatinine), Child-Pugh Score (for hepatic impairment) and, β -HCG (for females of child bearing potential only) and pelvi-abdominal Ultrasound & others.

- Presence of any signs/symptoms of post-operative wound infection such as redness, fever or wound discharge will be recorded (in case of post-operative subjects)

2- Follow-up 1 Visit:(Day 8):

- On-treatment assessments include physical examination, vital signs, AEs, SAEs, concomitant medication and study drug dosing compliance
- Days for complete healing will be checked
- Complete resolution, improvement, failure or relapse of Pelvi- abdominal infection
- Presence of any signs/symptoms of post-operative wound infection such as redness, fever or wound discharge will be recorded (in case of post-operative subjects)

3- Follow-up 2 Visit & End of study visit (Day 15):

- Assessments include physical examination for vital signs, AEs, SAEs, concomitant medication, and study drug dosing compliance
- Pelvi-abdominal Ultrasound and others will be done, if needed upon Physician's decision.
- Days for complete healing will be checked
- Complete resolution, improvement, failure or relapse of Pelvi- abdominal infection
- Presence of any signs/symptoms of post-operative wound infection such as redness, fever or wound discharge will be recorded (in case of post-operative subjects)
- Safety laboratory tests (including Total Leucocytic count, Liver enzymes (SGOT & SGPT), Total Bilirubin and S. Creatinine)
- The End of Study Form must be completed.

10.3 Variables:

10.3.1 Primary Endpoints:

1- *Primary Safety:*

Incidence of serious/non-serious adverse events

2- *Primary Efficacy:*

- Complete resolution for pelvi-abdominal infection based on pelvi-abdominal ultrasound and others and/or clinical response
- Complete healing of post-operative wounds

10.3.2 Secondary Endpoints:

1- *Secondary Safety:*

- Presence of any signs/symptoms of post-operative wound infection such as redness, fever or wound discharge.
- Change in Total leukocytes count and Liver enzymes (SGOT, SGPT), between baseline (visit 1) to End of study visit (Follow up 2 visit)

-

2- *Secondary Efficacy:*

- Describe complete resolution, improvement, failure or relapse of pelvi- abdominal infection based on pelvi-abdominal ultrasound and others and or clinical response.
- Days for complete healing of post-operative wounds after 8 days of treatment (Follow-up 1 V) & 15 days of treatment (End of study visit) between the 2 groups

10.4 Data Sources:

All visits assessments will be kept in the source files for each patient and in CRF, which will be verified by the CRA responsible.

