Also, the most common postoperative complications are postoperative fever, postoperative infection, atelectasis, embolism and Deep Vein Thrombosis (DVT). Postoperative infections include postoperative sepsis, urinary tract infection, chest infection, peritonitis, pelvic abscess, and surgical site infection. The highest incidence of postoperative complications is between one and three days after the operation. However, specific complications occur in the following distinct temporal patterns: early postoperative, several days after the operation, throughout the postoperative period and in the late postoperative period. [10]

Pelvic inflammatory disease (PID) is one of pelvi-abdominal infections that ranges from acute salpingitis to salpingo-oophoritis and ultimately pelvic abscess, if the disease process proceeds unabated. Morbidity is high, 20% of affected women become infertile, [11] 30% develop chronic pelvic pain and around 1% of those who conceive have an ectopic pregnancy. [12] There are neither pathognomonic symptoms nor specific laboratory tests to diagnose PID. However, specimens from the vagina and cervix should be taken for direct microscopy, culture and sensitivity prior to starting empirical treatment. [13] In the absence of generalized peritonitis or septicemia, most PID patients may be treated initially with oral antimicrobials. When intravenous antimicrobials are initiated, they should be continued for 24 hours after clinical response before converting to oral therapy. A 14-day course is recommended for adequate treatment. Surgical intervention may be required to either confirm the diagnosis of PID or surgical drainage of pelvic abscesses. Also, it should be considered in the following conditions: clinical failure with oral therapy, severe PID, inability to tolerate an oral regimen and in pregnancy. [12 - 13]

7 Rationale & Correlative Studies

7.1 Rationale:

Ciprofloxacin® (Ciprofloxacin & Metronidazole) is active against a broad spectrum of obligate anaerobic bacteria, including *Bacteroides* Species (spp.), *Fusobacterium* spp., *Clostridium* spp., *Treponema* spp. and various anaerobic cocci. The action is trichomonocidal and bactericidal. So, it is indicated in the treatment of Pelvi-abdominal caused by Gram negative bacteria such as *E. coli*, *Pseudomonas aeruginosa*, *Proteus mirabilis*, *Klebsiella pneumoniae*, or *Bacteroides fragilis* or others.

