8.6 Primary Safety analysis

A. Number of participants experiencing Serious Adverse Events (SAEs). [Time Frame: visit 1 to End of study visit].

- Frequency distribution (number & percent) of occurrence of SAEs necessitating a change or discontinuation of treatment. Chi² test will be used to determine p-value and significance between the 2 groups.

- Frequency distribution (number & percent) of type and severity of SAEs. Chi² test will be used to determine *p*-value and significance between the 2 groups.

B. Number of participants experiencing Adverse Events (AEs) leading to permanent discontinuation of the study drug. [Time Frame: visit 1 to End of study visit].

- Frequency distribution (number & percent) of causes of treatment discontinuations. Chi² test will be used to determine *p*-value and significance between the 2 groups.
- Frequency distribution (number & percent) of occurrence of AEs necessitating a change or discontinuation of treatment. Chi² test will be used to determine *p*-value and significance between the 2 groups.
- Frequency distribution (number & percent) of type and severity of AEs. Chi² test will be used to determine *p*-value and significance between the 2 groups.

8.7 Primary Efficacy analysis:

A. Complete resolution for Pelvi- abdominal infection based on pelvi-abdominal Ultrasound

- Frequency distribution (number & percent) of complete resolution for pelvi-abdominal infection. Chi² test will be used to determine *p*-value and significance between the 2 groups.

B. Complete healing of the post-operative wounds [Time Frame: Follow-up 1 V to End of study visit].

- Frequency distribution (number & percent) of complete healing of the post-operative wounds. Chi² test will be used to determine *p*-value and significance between the 2 groups.
- Frequency distribution (number & percent) of incomplete healing of the post-operative wounds. Chi² test will be used to determine *p*-value and significance between the 2 groups.
- Frequency distribution (number & percent) of no healing of the post-operative wounds. Chi² test will be used to determine *p*-value and significance between the 2 groups.

8.8 Secondary Safety analysis:

A. Presence of any signs/symptoms of post-operative wound infection such as redness, fever or wound discharge [Time Frame: visit 1 to End of study visit].

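### Rescue treatment for the index infection is not classified in the primary resolution endpoint, so a rescued failure is probably dropped from the efficacy analysis, or possibly scored as resolved

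*Protocol*

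**What the plan says.** The primary efficacy endpoint for infection (Protocol 10.3.1, repeated in SAP 5.1.2) is "Complete resolution for pelvi-abdominal infection based on pelvi-abdominal ultrasound and others and/or clinical response". It describes the patient's state and sets no condition on what other treatment was given. The analysis in Protocol 10.7.7 A and SAP 8.7 A is "Frequency distribution (number & percent) of complete resolution for pelvi-abdominal infection" with a chi-square test. SAP Table 9 has only two rows, complete and incomplete resolution.

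Failure appears only in the secondary endpoint (Protocol 10.3.2): "Describe complete resolution, improvement, failure or relapse of pelvi- abdominal infection based on pelvi-abdominal ultrasound and others and or clinical response". Neither document defines it or links it to rescue.

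On other treatment, Protocol 8.8 states that "Investigators may prescribe any concomitant medications or treatments deemed necessary to provide adequate supportive care except for those listed in the exclusion criteria". The next sentence reads "If these are required, the participant will be withdrawn". The exclusion criteria (Protocol 10.2.2, SAP 3.2) name "any other antibiotics during the previous two weeks, rather than IV treatment in the first post-operative 48 hours" in criterion 2, surgery after oral antibiotics have failed in criterion 3, and a list of interacting drugs in criterion 5. Protocol 10.2.3 gives reasons for which the investigator may discontinue a participant. These include progression that requires study medication to stop (4), an SAE (7), and "Subjects which have Cholecystitis and it will be operated upon" (9).

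Protocol 10.7.1 and SAP 8.1 limit every efficacy analysis to patients who completed without protocol violation.

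**The concern.** In an antibiotic trial, a need for another antibacterial, or for drainage or surgery, to clear the treated infection is usually direct evidence that study treatment failed. Here the endpoint looks only at the final state, and nothing says how such a patient counts.

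If rescue is common and similar in both arms, resolution rates rise and a true difference between the arms shrinks. If readiness to rescue differs between the arms, a difference can appear where none exists. The second risk matters here because the trial is open label: whoever decides on rescue, on withdrawal and on the outcome category knows the treatment arm.

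**Working it through.** **1. The plan's own figure.** Protocol 10.5.1 gives 312 patients, 80% power, alpha 5% and a margin of 2 points, and cites rates of 74% and 63%. With one-sided alpha 5%, test rate 74% and control rate 63%:

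n per arm = (1.645 + 0.842)² × (0.74×0.26 + 0.63×0.37) / (0.74 − 0.63 + 0.02)² = 6.18 × 0.4255 / 0.0169 ≈ 155.7, rounded up to 156, so 312 in total.

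The figure is reproduced. I use 74% and 63% below only as the documents' own rates. Whether they suit this comparison is a separate question.

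**2. What happens to a rescued patient.**

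- *Withdrawn.* This follows if 8.8 and exclusions 2–3 are read as applying during treatment, or if the investigator uses 10.2.3. The patient is then not a completer and leaves the efficacy analysis, counted neither as success nor as failure.
- *Kept in.* Exclusions 2 and 3 are worded for status at entry, so they may not reach treatment started later. The 10.2.3 reasons are discretionary. A patient who is not withdrawn, not called a protocol violator and well at Day 15 meets the wording of complete resolution.

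On neither route does the plan require the patient to be counted as not resolved.

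**3. Formulas.** Let p be the true resolution rate on study drug alone, and r the share of failures that are rescued and then cured. The documents give no r, so every value is an assumption. All other failures are taken to stay in as not resolved.

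- Counted as resolved: p + (1 − p)r
- Dropped: p / [1 − r(1 − p)]

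**4. Equal rescue, true rates 63% v 74% (a true 11-point deficit).**

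| r | Dropped | Apparent deficit | Counted as resolved | Apparent deficit |
|---|---|---|---|---|
| 25% | 69.4% v 79.1% | 9.7 | 72.25% v 80.5% | 8.25 |
| 50% | 77.3% v 85.1% | 7.8 | 81.5% v 87.0% | 5.5 |
| 75% | 87.2% v 91.9% | 4.7 | 90.75% v 93.5% | 2.75 |

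At r = 50%, for example: dropped, 0.63/0.815 = 0.773 and 0.74/0.87 = 0.851; counted, 0.63 + 0.37×0.5 = 0.815 and 0.74 + 0.26×0.5 = 0.870.

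**5. Unequal rescue, both true rates 74%, r = 50% v 30%.**

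- Dropped: 0.74/0.87 = 85.1% v 0.74/0.922 = 80.3%, a spurious 4.8 points.
- Counted: 0.74 + 0.26×0.5 = 87.0% v 0.74 + 0.26×0.3 = 81.8%, a spurious 5.2 points.

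Both favour the arm with more rescue, and both exceed the 2-point margin.

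**6. Effect on a margin-based test** (156 randomised per arm, margin 2 points, one-sided 5%, r = 50% in both arms). If the test drug is truly 74% v 63%, power falls from 80% to 65% (dropped) or 57% (counted). If it is truly 63% v 74%, the chance of passing is 0.2% (dropped) or 0.6% (counted).

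**The case against.** A reader who stops at the first sentence of 8.8 might infer that rescued patients remain in the analysis and are counted as successes. The documents do not support that as the general case. The very next sentence requires withdrawal when an excluded treatment is needed. Exclusion 3 and discontinuation reasons 4 and 7 can also apply, and hospitalisation or its prolongation is an SAE under Protocol 13.2. Efficacy is restricted to completers without violation. The permission in 8.8 is for supportive care, and a replacement antibacterial for the index infection fits that description poorly. All of this stands, and it makes removal from the analysis the likelier outcome. It does not close the gap, because the exclusions are worded for entry, the 10.2.3 reasons are discretionary, and removal also loses the failure.

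A reader might also infer that surgical rescue is deliberately treated differently by diagnosis, since only operated cholecystitis is named while Protocol 6 lists "clinical failure with oral therapy, severe PID, inability to tolerate an oral regimen and in pregnancy" as situations in which to consider surgery for PID. But the 10.2.3 list is open-ended, and section 6 is background. The passages are unclear together; they do not establish two different rules.

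The investigator records failure or relapse at Day 8 and Day 15, so a rescued patient could be recorded as a failure at Day 8. That is possible, but the category is undefined and secondary, and nothing carries it into the primary endpoint.

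Finally, dilution does not simply help a non-inferiority claim. Under the plan's implied advantage it costs power. With a true 11-point deficit and equal rescue of 50%, a false pass remains below 1%. The analysis sections also name only chi-square tests and no test against the margin. These points stand: the main effects are a distorted estimate and exposure to unequal rescue.

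**Conclusion.** The concern holds in a limited form. Neither document makes a non-study antibacterial, or unplanned drainage or surgery, for the index infection a failure of primary resolution. The rescued patient is most likely dropped from the efficacy analysis, and may be scored as resolved where withdrawal is not triggered or not applied. In both cases the treatment failure disappears.

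The size depends on a rescue rate that the documents do not give. At an assumed 50% in both arms, a true 11-point deficit shows as 7.8 points (dropped) or 5.5 (counted). At an assumed 50% v 30% with no true difference, a spurious 4.8 or 5.2 points appears. If rescue is rare, the effect is small. It would be wrong to conclude that the plan generally counts rescued patients as cures. This is a cheap improvement rather than a fatal flaw.

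**What to change.** 1. In Protocol 10.3.1 and 10.7.7 A, and SAP 5.1.2 and 8.7 A, state that a patient who after the first dose receives a non-study systemic antibacterial for the index infection, or unplanned drainage or surgery for it, is counted as not resolved, in both arms alike.
2. In Protocol 10.7.1 and SAP 8.1, state that such patients stay in the efficacy analysis as not resolved even if withdrawn, and are not removed as non-completers or protocol violators. Without this, the first change has no effect on withdrawn patients. The classification is settled at the time of rescue, so it does not depend on later follow-up.
3. Record rescue procedures with date and reason in the CRF, as 8.8 already requires for medications.
4. The sponsor should reconcile 8.8, exclusions 2–3 and 10.2.3 (4) and (9) on whether non-study antibacterials, and surgery for any diagnosis, lead to withdrawal. This point concerns classification in the analysis only and proposes no rule on who receives rescue or is withdrawn.

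The cost is protocol and SAP wording, minor extra CRF recording, and a somewhat lower resolution rate in both arms.
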